### **5.5. Lifestyle guidelines**

It is highly unlikely that the patient population included in PIVOTALboost will be at risk of fathering a child. However if this is a possibility for any individual patient, this and sperm banking should be discussed and the patient should be advised to use barrier protection and avoid conception for 12 months after treatment.

## **6. SCREENING**

### **6.1. Screening log**

All participating sites will be required to keep a log of all participants who are considered fit for radical radiotherapy (following discussion at the MDT) and are potentially eligible for this study. The information collected on the log will include:

- Date patient identified
- Screening outcome (patient approached/accepted participation/declined participation)
- Reasons for not approaching / declining participation (if available)
- Details of suitability for boost (if applicable)
- Trial ID (if applicable)

This information will be used by the TMG to monitor recruitment activity. No patient identifiable data will be sent to ICR-CTSU at this stage.

### **6.2. Procedure for obtaining informed consent**

The Principal Investigator (or designated individual) must ensure that each trial patient is fully informed about the nature and objectives of the trial and possible risks associated with participation. Participants should be given the current REC approved PIVOTALboost patient information sheet for their consideration. Patients should only be asked to consent to the study after they have had sufficient time to consider the trial, and the opportunity to ask any further questions.

No protocol required assessments should be conducted until the PIVOTALboost consent form has been signed and dated by both the patient and the Investigator, unless they are performed routinely as part of standard patient care.

Patients who consent to PIVOTALboost will be asked to consent to participate in the Patient Reported Outcomes (PRO) and future translational sub-studies. Patients should be made aware that participation in the sub-studies is entirely voluntary. Refusal to participate in the sub-studies will not result in ineligibility to participate in the main clinical trial and will not impact the medical care received.

Confirmation of the patient's consent and the informed consent process must be documented in the patient's medical notes. A copy of the signed consent form should be provided to the patient and the original retained in the investigator site file, which must be available for verification by ICR-CTSU study staff.

### **6.3. Participation in other research**

Patients who fulfil the eligibility criteria will be given the opportunity to participate in PIVOTALboost even if they have participated in other research prior to recruitment. Participation in other research will be considered on a case-by-case basis by the Trial Management Group.

Participation in the ICR-CTSU study within a trial investigating electronic collection of patient reported outcomes, SPRUCE, is permitted.

## **7. RANDOMISATION**

Patients must be randomised centrally by the trials unit (ICR-CTSU) before trial treatment can commence.

Patients should be randomised by telephoning ICR-CTSU on **[name]**

or emailing [[contact]](mailto:[contact]) to request a call back\*

09.00-17.00 (UK time) Monday to Friday

\*During the COVID-19 pandemic, in periods when the ICR-CTSU are working remotely, randomisations may be managed via email, [[contact]](mailto:[contact]). Please refer to the most recent guidance provided by the trials team.

**Randomisation should take place as close to the start of radiotherapy treatment as possible.** An eligibility and randomisation checklist must be completed prior to randomisation.

The following information will be required at randomisation:

- Name of hospital, consultant and person randomising patient
- Confirmation that patient has given written informed consent for trial and for any sub-studies;
- Confirmation that patient is eligible for the trial by completion of the eligibility checklist
- Patient's full name, hospital number, date of birth, postcode and NHS/CHI number
- Randomisation option (2 arms or 4 arms), NCCN risk group (intermediate or high), boost volume identified at staging MRI (suitable for a focal boost or not) and, in case of the 4-arm randomisation, type of boost (whole gland HDR or focal HDR or focal IMRT).

The caller will be given the patient's unique randomisation number (Trial ID) and treatment allocation (see section 14.2).

ICR-CTSU will send written confirmation of trial entry to the data management contact at the recruiting centre.

PIVOTALboost arm B closed to recruitment in Q2 2022

## **8. TRIAL ASSESSMENTS**

### **8.1. Screening assessments**

The following screening assessments should be conducted prior to randomisation

- Complete history.
- DRE and physical examination (only if clinically indicated).
- Assessment of performance status, using WHO scale (see Appendix 1).
- Assessment of fitness using the Adult Comorbidity Evaluation (ACE-27) scale and American Society of Anaesthesiologists (ASA) scale (see Trial Guidance Notes).
- Eligibility for A vs B, and A vs B vs C1 vs D1:  
Radiological assessment of prostate cancer. Ideally within 2 months and within a maximum of 12 months prior to randomisation and 6 months prior to starting ADT; this includes a mpMRI scan of the prostate and pelvis and at least one of the following: bone scan, WB MRI, MRI spine, Choline PET, PSMA PET. If patients are longer than 6 months on ADT because of the COVID-19 pandemic, the imaging needs to be performed in 6 months prior to starting ADT.

PIVOTALboost arm B closed to recruitment in Q2 2022.

- Eligibility for A vs B vs C2 vs D2:  
Radiological assessment of prostate cancer. Ideally within 2 months and within a maximum of 12 months prior to randomisation and starting ADT; this includes a mpMRI scan of the prostate and pelvis and at least one of the following: bone scan, WB MRI, MRI spine, Choline PET, PSMA PET. If the patient is offered the boost randomisation arms (A vs B vs C2 vs D2) a **pre-biopsy mpMRI is mandatory**. If the pre-biopsy mpMRI has occurred more than 6 months prior to randomisation or starting ADT a repeat mpMRI is strongly recommended prior to treatment to exclude progressive disease in the interim. If patients are longer than 6 months on ADT because of the COVID-19 pandemic, the imaging needs to be performed in 6 months prior to starting ADT; a pre biopsy mpMRI remains mandatory. Please see definition of a suitable focal boost volume on page 16, Box 1.

PIVOTALboost arm B closed to recruitment in Q2 2022.

- PSA test prior to the commencement of ADT (as per eligibility criteria should be <50ng/ml)
- Full blood count, Urea & Electrolytes. For patients affected by the COVID-19 pandemic, results taken prior to or at planning are acceptable.
- Baseline symptoms will be assessed using Common Toxicity Criteria for Adverse Event Reporting (CTCAE) version 4.03 and RTOG bladder and bowel toxicity scoring (conducted within 4 weeks prior to randomisation).
- If the patient has consented to the PRO sub study, completion of the following questionnaires (within 4 weeks prior to randomisation).:
  - ALERT-B (Assessment of Late Effects of RadioTherapy - Bowel) screening tool.
  - Gastrointestinal Symptom Rating Scale (GSRS)
  - IIEF-5 Questionnaire (SHIM)
  - International Prostate Symptom Score (IPSS)
  - Expanded Prostate Index Composite-26 (EPIC-26) Short Form questionnaire
  - EQ-5D

Where participating sites are taking part in the SPRUCE study (REC Ref: 21/WM/0223) PIVOTALboost participants should be approached about SPRUCE and enrolled following completion of the PIVOTALboost

baseline booklet and randomisation into PIVOTALboost. All PIVOTALboost follow up QL questionnaires will be administered directly to participants by ICR-CTSU for patients participating in SPRUCE.

### **8.1.1. Staging multiparametric MRI scan**

A minimum of T1W, T2W and one other functional sequence should be performed up 12 months prior to randomisation. All images should be acquired using a 1.5 Tesla (or higher) MRI scanner with a body coil. Whether the staging MRI has been done pre or post biopsy will be collected.

## **8.2. Pre-treatment assessments**

The following assessments should be conducted within 14 days prior to or at RT planning:

- Assessment of pre-treatment symptoms (RTOG, CTCAE v4)
- PSA and testosterone (at least 2 months after starting ADT and prior to starting radiotherapy. For patients who have had multiple PSAs whilst on ADT, prior to starting radiotherapy, please record the one closest to the radiotherapy start date.
- For patients randomised to HDR, ECG and clotting required.

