## **10.5. Radiotherapy planning and delivery**

All participants will be planned to receive 15 or 20 fractions of radiotherapy delivered daily. External beam radiotherapy planning will ideally be performed during month 2-4 (maximum 6) of ADT and radiotherapy treatment will commence within 6 months of ADT. Delays to radiotherapy (with extended ADT) due to COVID19 clinical management strategies are permitted and should be documented (details of how to do this are given in the Trial Guidance Notes).

If participants are allocated to a HDR implant, the HDR implant will be scheduled 14-21 days before starting EBRT (EBRT will consist of 15 fractions for arm C1 or C2 and 20 fractions for arm D1 or D2). EBRT planning will be carried out before or after the HDR implant. EBRT is started two to three weeks after the HDR (day 0). However, if it is standard protocol in the unit, HDR implant can be scheduled 2-3 weeks after completion of EBRT subject to RTQA approval. The first acute toxicity assessment occurs during week 1 of EBRT.

Radiotherapy planning and outlining should be carried out in accordance with the guidelines in the current version of the radiotherapy planning and delivery guidelines, available in the PIVOTALboost site investigator file and on request from ICR-CTSU ([contact]).

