#### 12.5. Reporting Adverse Events to ICR-CTSU

Any toxicity, sign or symptom that occurs after commencement of study treatment and within 30 days of the last administration of study treatment, which is not unequivocally due to progression of disease, should be considered an AE. All AEs must be reported on the relevant toxicity, sign or symptom eCRF.

The severity of AEs should be graded according to CTCAE v4 and RTOG criteria. For each toxicity/sign/symptom, the highest grade observed since the last visit should be reported.

Whenever one or more toxicity/sign/symptom corresponds to a disease or a well-defined syndrome only the main disease/syndrome should be reported.

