### **A3. RTOG Toxicity Scales**

#### **Instructions**

1. Toxicity grade should reflect the most severe degree occurring during the evaluated period, not an average.
2. When two criteria are available for similar toxicities, the one resulting in the more severe grade should be used.
3. Toxicity grade = 5 if that toxicity caused death of the patient.
4. An accurate baseline prior to start of therapy is necessary.

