#### **Acute Toxicity [To be used from baseline to 18 week follow up visit]:**

##### **Bladder changes/cystitis/frequency:**

Grade 0: No symptoms

Grade 1: Frequency of urination or nocturia twice pretreatment habit/dysuria, urgency not requiring medication.

Grade 2: Frequency of urination or nocturia which is less frequent than every hour. Dysuria, urgency, bladder spasm requiring local anaesthetic.

Grade 3: Frequency with urgency and nocturia hourly or more frequently/dysuria, pelvic pain or bladder spasm requiring regular, frequent narcotic/gross haematuria with/without clot passage.

Grade 4: Haematuria requiring transfusion/acute bladder obstruction not secondary to clot passage, ulceration or necrosis.

Grade 5: Death directly due to radiation morbidity.

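### For patients given HDR before EBRT, the pre-treatment toxicity score is tied to RT planning and so can be taken after the implant and still be labelled baseline

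*Protocol*

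**What the plan says.** Section 8.2 lists the pre-treatment assessments (RTOG/CTCAE symptoms, PSA and testosterone, and ECG and clotting for HDR patients) under one timing rule: "The following assessments should be conducted within 14 days prior to or at RT planning".

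Section 10.5 fixes the usual HDR sequence: "If participants are allocated to a HDR implant, the HDR implant will be scheduled 14-21 days before starting EBRT". It then leaves the order of planning open: "EBRT planning will be carried out before or after the HDR implant". It also permits the reverse sequence: "HDR implant can be scheduled 2-3 weeks after completion of EBRT subject to RTQA approval". On toxicity forms it says: "The first acute toxicity assessment occurs during week 1 of EBRT".

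Section 12.2 counts the HDR implant as part of the start of study treatment. In section 9 the pre-treatment column is marked in two rows, one for baseline signs and symptoms and one for acute toxicity. Appendix 3 instructs: "An accurate baseline prior to start of therapy is necessary". Section 12.5 says of each toxicity that "the highest grade observed since the last visit should be reported". Section 13.6 summarises acute toxicity by time point and as the worst grade reported during radiotherapy.

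Section 8.1 separately requires RTOG and CTCAE scoring in every arm within 4 weeks before randomisation.

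**The concern.** The anchor for the pre-treatment score is planning, but for HDR-first patients planning need not precede the first radiation dose. Nothing in section 8.2 requires the symptom score to come before the implant. A compliant site can therefore record early implant symptoms as pre-treatment symptoms. By the section 12 definitions, the same symptoms are adverse events occurring after study treatment began.

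The consequence does not depend on any change-from-baseline analysis. The week-1 EBRT form looks back only to the previous visit. If that visit was a post-implant planning visit, a reaction that came and went before it appears only on a form labelled baseline. If the visit preceded the implant, week 1 picks the reaction up. What is collected thus depends on local planning order, and only among HDR patients in the boost arms. Any loss lowers the recorded toxicity of HDR, while the primary objective includes similar levels of bladder and bowel side effects.

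**Working it through.** The protocol states no figure that depends on this timing, so there is nothing to reproduce. The check is to count the calendar that sections 8.2 and 10.5 allow.

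**Inputs.** Day 0 is the first EBRT fraction. The implant day h runs from -21 to -14 (section 10.5). The planning day p, when planning follows the implant, runs from h+1 to -1. That p may be any of these days is an assumption, because the protocol gives no minimum lead time. The assessment window runs from p-14 to p (section 8.2).

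**Permitted pairs.** For each h there are -1-h planning days: 20, 19, 18, 17, 16, 15, 14 and 13. The sum is 132.

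**Pairs with a post-implant day in the window.** The window always includes p, and p is later than h, so this is all 132.

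**Pairs with no day before the implant day.** This needs p-14 ≥ h, that is, planning at least 14 days after the implant. For h = -21 to -14 the counts are 7, 6, 5, 4, 3, 2, 1 and 0. The sum is 28. In 7 of these (p-14 = h, once for each h from -21 to -15) the window opens on the implant day itself, so a score earlier that same day is still possible. In the other 28-7 = 21 it is not.

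**Remaining pairs.** In 132-28 = 104, a score before the implant day is possible but not required.

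**Sensitivity to lead time.** Suppose, as an assumption, that planning must fall on day -7 or earlier. The pairs become 14+13+12+11+10+9+8+7 = 84. Only h = -21 with p = -7 still has no earlier day, so 1 of 84. The case in which an earlier score is impossible is therefore sensitive to lead time. The case in which a post-implant score is allowed is not: it holds for every pair.

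All of these are counts of calendar options, not of patients.

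**Effect on the forms.** Take an implant on day -21 with planning and scoring on day -7. The week-1 form then reaches back only to day -7, so it leaves out -7-(-21) = 14 days after the implant. A reaction in that interval is recorded, if at all, on the pre-treatment form. Section 9 marks that visit both as baseline and as acute toxicity and does not say which use governs.

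**Effect on grading.** The reference to usual habit, "Frequency of urination or nocturia twice pretreatment habit", appears only in acute bladder grade 1. Bladder grade 2 and above is defined in absolute terms, so a raised baseline does not move the grade 2 threshold.

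**The case against.** The strongest defence is that a clean baseline already exists. Section 8.1 requires RTOG and CTCAE scoring before randomisation in every arm, which can satisfy Appendix 3. This stands. A reader might infer that HDR patients have no valid baseline, and the document does not support that. The screening score is older, up to about 4+8 = 12 weeks at the start of radiotherapy on the ideal timeline of section 10.2, but it is valid. It does not, however, restore a reaction missing from the on-treatment forms.

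Second, the title of section 8.2, the wording of the item and the presence of ECG and clotting all suggest that a pre-implant visit was intended. That is plausible, but the text does not say so and section 10.5 permits the opposite.

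Third, section 12.5 requires any toxicity after treatment starts to be reported as an adverse event, and section 9 also marks the pre-treatment visit as an acute toxicity assessment. Both limit the loss. Neither says that a post-implant pre-treatment score enters the worst grade during radiotherapy.

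Fourth, a reader might infer that the PSA baseline is contaminated and the primary endpoint affected. Section 8.2 already limits the PSA sample to before radiotherapy starts. It could be post-implant only if radiotherapy is read as EBRT alone. Biochemical failure is measured from the post-treatment nadir, not from this value.

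Fifth, section 12.2 also counts fiducial marker insertion as the start of study treatment, and markers may be used in any arm. On that definition, scoring after the start of treatment is not unique to HDR. The differential effect described here comes from the implant.

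**Conclusion.** The point holds in limited form. Sections 8.2, 9 and 10.5 together allow a score labelled pre-treatment to be taken after the HDR implant. With planning after the implant, this is possible in all 132 permitted day pairs, and in 28 of them no earlier day is available, assuming that planning may fall on any day up to the eve of EBRT. The resulting error is a possible understatement of worst acute toxicity during radiotherapy for some HDR patients.

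It does not extend to arms A and B, focal IMRT boosts, HDR given after EBRT, or HDR patients scored before the implant. A reader might infer bias in the safety rule of section 13.7 (27 or more of 119 with grade 2 or worse at 18 weeks). That rule uses absolute grades at week 18 and is essentially unaffected. A reaction dropped from the forms could still be missing from a worst-grade summary.

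The number of patients cannot be derived. Appendix 4 projects 2 × (212+246) = 916 patients in arms C and D, but that total includes focal IMRT patients. The protocol gives neither the HDR share, nor the share planned after the implant, nor how many of those were scored afterwards. Any count would rest on guesses. This is worth correcting at the next amendment and is no threat to the primary analysis.

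**What to change.** - In section 8.2 and the section 9 schedule, time the pre-treatment RTOG/CTCAE score to before the HDR implant or the first EBRT fraction, whichever comes first.
- For patients already scored on or after the implant, use the screening score as baseline and count the post-implant score as acute toxicity.
- State that the PSA limit of before radiotherapy includes the implant. This is a clarification only.
- The HDR ECG and clotting share the planning anchor, so sections 8.2 and 10.5 must be reconciled for their timing too.

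The cost is amendment wording and a date check on the eCRF. Some HDR patients may need to be scored at a different contact from the planning visit.

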## **8.3. On-treatment assessments**

- Acute toxicity assessment (RTOG, CTCAE v.4) weekly during treatment
- IPSS (at the end of week 4 of treatment).

## **8.4. Post radiotherapy assessments**

Any follow up visits may be done as a telephone consultation, at the discretion of the treating clinician.

### **8.4.1. 6, 8 and 12 weeks from first external beam radiotherapy fraction**

- Acute toxicity assessment (RTOG, CTCAE v.4)
- IPSS

### **8.4.2. 18 weeks from first external beam radiotherapy fraction**

- Acute toxicity assessment (RTOG, CTCAE v.4)
- IPSS
- QL questionnaires (EPIC-26 & EQ-5D).

### **8.4.3. 6, 12, 18, 24, 36, 48 and 60 months (from first radiotherapy fraction)**

- Late toxicity assessment (CTCAE v.4 and RTOG)
- QL questionnaires (EPIC-26, EQ-5D, ALERT-B, GSRS, IIEF). These will be sent to the patient's home address direct from ICR-CTSU, once patient status is ascertained.
- PSA
- NHS resource usage assessment.

### **8.4.4. Annually thereafter**

Patients will not be required to undergo any trial specific investigations; however data will be requested annually from standard follow up visits relating to:

- Assessment of disease status
- PSA
- Survival
- Second primary cancers

- NHS resource usage assessment.

These data items may also be obtained, with patient consent, through linkage to routine data sources e.g. to datasets held by the National Cancer Registration and Analysis Service (NCRAS).

### **8.5. Procedure at PSA failure or disease recurrence**

At PSA failure or recurrence participants should be treated according to the local Principal Investigator's clinical judgement. It is recommended to observe PSA failure initially. If appropriate and / or the patient is considered for local salvage therapies, local control should be assessed by mpMRI imaging, PSMA PET and / or biopsies. Staging with bone scan, MRI and CT scan is recommended prior to re-commencing hormone therapy if either the PSA doubling time is <6 month and PSA >2ng/ml, or PSA >10-20ng/ml.

### **8.6. Discontinuation from study treatment**

Participants may discontinue from study treatment at any time at their own request, or they may be discontinued at the discretion of the Principal Investigator. Reasons for withdrawal should be documented and may include:

- Disease recurrence or PSA failure
- Unacceptable toxicity
- Co-morbidities

Participants who discontinue treatment should continue to be followed up in accordance with the protocol.

### **8.7. Discontinuation from follow-up**

If a patient withdraws from further follow-up a trial deviation form should be submitted to ICR-CTSU stating whether the patient has withdrawn consent for information to be sent to the ICR-CTSU or whether they simply no longer wish to attend trial follow up visits. In the very rare event that a patient requests that their data is removed from the study entirely, the implications of this should be discussed with the patient first to ensure that this is their intent and, if confirmed, ICR-CTSU should be notified in writing.

## 9. SCHEDULE OF ASSESSMENTS

Visit/Assessment	Screening (pre-randomisation)	Pre-treatment	External beam treatment week 1-4	Week 6, 8, 12	Week 18	6, 12, 18, 24, 36, 48, 60 months	Annually thereafter	PSA failure or disease recurrence
Histological confirmation of prostate cancer	X							
Complete history and physical examination (physical examination & DRE if clinically indicated)	X							
WHO PS, ASA score, ACE-27 score	X							
Radiological assessment (multi-parametric MRI scan, and one of the following: bone scan, WB MRI, MRI spine, Choline PET, PSMA PET)	X 							
PSA	X	X 				X	X	X
FBC, U+E	X							
Testosterone		X 						
Clotting and ECG		X 						
Baseline signs & symptoms (RTOG, CTCAE v.4)	X	X						
Acute toxicity assessment (RTOG, CTCAE v.4)		X	X	X	X			
QL questionnaires – IPSS	X		X 	X	X			
QL questionnaires – EPIC & EQ-5D	X				X	X		
QL questionnaires – ALERT-B, GSRs, IIEF-5 (SHIM)	X					X		
Late toxicity assessment (RTOG, CTCAE v.4)						X	X	
Assessment of disease status						X	X	X

Screening radiological assessment should take place ideally within 2 months and within a maximum of 12 months prior to randomisation AND no more than 6 months prior to starting ADT. For details how patients are screened and assessed during the COVID pandemic, please refer to section 8.1 and 8.2

Only for patients randomised to HDR.

IPSS questionnaire to be completed only at the end of week 4.

at least 2 months after starting ADT and prior to starting radiotherapy. For patients who have had multiple PSAs whilst on ADT, prior to starting radiotherapy, please record the one closest to the radiotherapy start date.

